#### **12.2.** Screening Assessments for all Schedules

Any subjects deemed possibly eligible for participation will be recruited and assigned a screening number. Before screening assessments are conducted, the PI or designated representative will explain the protocol procedures, including timing; the expected and unknown risks and possible benefits; and answer all subject's questions and concerns. The informed consent procedure should be documented in the source record and include at least the following: (1) subject screening number; (2) date and time; (3) person performing the consent procedure; (4) persons present during the consent procedure and their relationship to the subject or the study; (5) document any questions asked or concerns expressed by subject or subject's representative(s); (6) confirmation that subject understands that participation is voluntary and can withdraw at any time without penalty, that the protocol is experimental, that no particular outcome can be assured or is known, that there is the possibility of side-effects some of which may be serious, and that the protocol requires commitment of significant time to visit clinic and participate in telephone interviews. Subsequently, the subject must sign and date and receive a copy of an informed consent document that was approved by the Institution Review Board (IRB) or Independent Ethics Committee (IEC) before any study specific procedure is performed. An additional signed copy should be retained and placed in the Study File.

Baseline assessments can be initiated up to two weeks prior to the first scheduled investigational product administration (Day -14) and must be completed at least 4 day prior to the scheduled investigational product administration (Day -4) due to formulation logistics and transits times. Results of tests or examinations performed as standard of care prior to obtaining informed consent and within 14 days prior to protocol Day 0 may be used, rather than repeating required tests. The following evaluations and procedures will be performed during screening:

- Written informed consent(s)
  - Study informed consent
- Complete medical history, including disease history (date of diagnosis, prior cancer therapy and surgery, tumor/node/metastasis staging at the time of diagnosis and study entry and pre-existing toxicities from previous therapies)
- Prior (within 30 days) and current concomitant medications
- Complete comprehensive physical examination, including the evaluation of any evidence of major depression and suicidal behavior (subject's previous suicide attempts and any suicidal ideations)
- Demographics
- Vital signs, including heart rate, respiration rate, blood pressure, temperature, pulse oximetry, and weight.
- EKG
- Blood draws for CBC, CMP, Total IgG and IgM, erythrocyte sedimentation rate, lipase, and CRP
- Pregnancy test (if applicable)
- Coagulation test (PTT, PT, INR)
- HLA baseline test
- ECOG performance score
- Baseline CT scan of head, chest, abdomen, and pelvis (w/ and w/o contrast). If brain involvement at baseline, subjects will be excluded. Future scans only require chest, abdomen and pelvis (unless symptoms are present which suggest possible brain metastasis). Subjects with medical conditions which contraindicate the use of contrast will be scanned without contrast. The baseline scan will be reviewed by an interventional radiologist for determination of a target lesion for cryoablation. An ultrasound study will be conducted on the target lesion(s) to determine feasibility of using ultrasound guidance for the procedure. The interventional radiologist must certify that a metastatic lesion exists in a location that can be safely approached percutaneously for image-guided cryoablation. This certification along with a summary report describing the target lesion will be sent to the referring PI and Sponsor.
- Tumor biopsy (mandatory). Place biopsy in the container provided by the Sponsor and send for pathology analysis

# **12.3.** Eligibility Determination (screening) for all Schedules (Study Site)

After all the baseline data are obtained (baseline H&P, laboratory and imaging data), the PI or designee will conduct a final assessment including opinion of the interventional radiologist regarding tumor accessibility for cryoablation and biopsy (subject need not be present) in

order to assure that the subject meets all inclusion/exclusion (IC/EC) criteria prior to the first investigational product administration (on or before Day -1). Subjects failing to meet IC/EC criteria after baseline assessment will be dropped from the study. A baseline assessment form will be filed by the PI with the Sponsor certifying either enrollment or drop status of the subject after baseline assessment.

Accepted subjects will be assigned a subject number by the Sponsor that will be used for all future reference to the subject.

#### **13. DISCONTINUATION CRITERIA**

#### **13.1.** EARLY DISCONTINUATION OF THE STUDY

The study may be discontinued due to clinical hold or other regulatory action. The Sponsor can discontinue the study at any time for any reason with appropriate notice to the study site and the IRB with oversight responsibility. The Sponsor can terminate the participation of the study site if the site is not conducting the protocol in accordance with the procedures defined in the approved protocol (i.e. protocol deviations, failure to ensure the quality of the data collected, etc.) or due to low rate of recruiting.

The DSMB can recommend termination of the study if they are of the opinion that the benefit/risk ratio has become adverse to the subject. The PI can terminate participation in the study if in the opinion of the investigator, information on the investigational product causes doubt as to the benefit/risk ratio for participation.

#### **13.2.** EARLY DISCONTINUATION OF INDIVIDUAL SUBJECTS

Subjects may discontinue participation in the study for the following reasons:

- Protocol violation
- Withdrawal of consent
- DLT event
- Non-compliance
- Changes in the subject's condition render the subject unacceptable for further treatment in the judgment of the Principal Investigator (the reason(s) must be documented)
- Subject becomes pregnant (withdrawal is required)
- Subject is lost to follow-up

After termination of study therapy, the subject will be treated as clinically indicated by the investigator. All subjects will be followed until resolution or stabilization of any study-related toxicity. If a subject is discontinued from all study therapy, the reason(s) for discontinuation should be documented in the subject's medical record and CRF/eCRF. A follow-up evaluation should be performed approximately 28 days after the last dose of study drug.

# **14. STUDY TREATMENT**

#### **14.1.** STUDY DRUG FORMULATIONS

AlloStim® is formulated T-StimTM cells that have been activated by adding CD3/CD28conjugated microbeads and packaged in a syringe. AlloStim® is prepared by thawing frozen, QC released T-StimTM cells and incubating the cells for 4 hours with Dynabeads® *ClinExVivo*TM CD3/CD28. The beads are mixed with the cells at a 2:1 bead to cell ratio. After 4 hours, the cells with the beads attached are harvested, washed and suspended in formulation buffer containing PlasmaLyteA® supplemented with 1% human serum albumin. The formulated cells with the beads still attached are then loaded in a syringe for infusion or injection. A sample from the syringe lot is tested for bacterial contamination with a Rapid Microbiological Method (RMM) with results available in 48 hours. The investigational product AlloStim® is formulated in syringes as follows:

- Intradermal (ID) dose:  $1 \times 10^7$  cells with  $2 \times 10^7$  beads in 1 ml in a 3 ml syringe
- Intravenous (IV) dose:  $3 \times 10^7$  cells with  $6 \times 10^7$  beads in 3 ml in a 10 ml syringe

#### 14.2. DRUG STORAGE AND RELEASE

The AlloStim® syringes are packaged in validated temperature-controlled containers and shipped by specialized courier service to the study site at least 48 hours prior to the protocol required treatment day.

Each shipment is accompanied by a Shipment Receipt Form and a Certificate of Analysis for product safety testing. Upon receipt, at the clinical site, the product is unpacked by a designated person(s) and immediately transferred to 2°C to 8°C (36°F to 46°F) storage. The syringe lot is quarantined at the study site until notification of Rapid Microbiological Method (RMM) release. The lot must pass RMM test, prior to release of each syringe to the clinic. The release must be documented on provided forms.

The AlloStim® is stable for 72 hours under refrigeration at 2°C to 8°C (36°F to 46°F). **DO NOT FREEZE.** Do not use AlloStim® after the expiry time and date that are printed on the label. If the AlloStim® is not administered and the expiry time and date have passed, the syringes should be discarded and another dose should be requested for use.

#### 14.3. DRUG PREPARATION PRIOR TO ADMINISTRATION

Prior to use, the AlloStim® is removed from storage and kept at room temperature for 15-45 minutes. The AlloStim® is stable for 90 minutes at room temperature. If the AlloStim® is not administered within 90 minutes window, the syringes should be discarded and another dose should be requested for use.

For each AlloStim® use, the study drug lot number, time and date the cells released to the clinic, incubation time at room temperature, administration date, time, and dose, injection site location (as applicable) should be documented in subject's medical records and provided forms.

### **14.4.** TREATMENT ADMINISTRATION

# 14.4.1. Intradermal Injection

Each ID injection contains  $1 \times 10^7$  AlloStim® cells formulated in 0.5ml of 1% human serum albumin in PlasmaLyteA. One pre-formulated 3 ml syringe of AlloStim® will be delivered to the study site per subject for the ID injection days.

For schedules A-1 and A-2, 0.5 ml of AlloStim® will be administered, and the remaining 0.5 ml will be discarded.

ID Injections shall be administered into the forearm (abdomen and deltoid areas can also be used) for schedule A-1 and A-3 on days 0, 7, 14, and 21, schedules A-2 and A-4 on days 0, 7, 14 and for schedule B, C, D, E and F on days 0, 3, 7, and 10. The injection on Day 3 must be in the same location as on days 0. The day 7 injection should be in different place than the day 0 and 3 injections and the day 10 injection in the same location as the day 7 injection. If the skin in the selected site is hardened, inflamed or otherwise not suitable for ID injection, select a different site. The site selected for each injection and the barcode sticker indicating the batch of the dose will be recorded on a provided form.

For the ID injection, the needle should be at a shallow angle, approximately 15 degrees (just under the skin). Some resistance should be felt, if not, the needle is likely too deep and should be pulled back until the bevel is barely under the skin. The plunger should be pressed slowly and a wheal or bubble should appear at the injection site. The longest diameter of the wheal will be recorded immediately following injection in the source document.

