## AlloStim®:

AlloStim® is formulated T-StimTM cells that have been activated by adding CD3/CD28conjugated microbeads and packaged in a syringe. AlloStim® is prepared by thawing frozen, QC released T-StimTM cells and incubating the cells for 4 hours with Dynabeads® *ClinExVivo*TM CD3/CD28. The beads are mixed with the cells at a 2:1 bead to cell ratio. After 4 hours, the cells with the beads attached are harvested, washed and suspended in formulation buffer containing PlasmaLyteA® supplemented with 1% human serum albumin. The formulated cells with the beads still attached are then loaded in a syringe for infusion or injection. A sample from the syringe lot is tested for bacterial contamination with a Rapid Microbiological Method (RMM) with results at 24 -48 hours. AlloStim® syringes are packaged in validated temperature-controlled containers and shipped by specialized courier service to the study site at least 48 hours prior to the protocol required treatment day for each enrolled subject. The syringe lots are quarantined at the study site until notification of RMM release. The cells are stable for at least 72 hours in this final formulation. AlloStim® is available in the following dosage forms:

- 1 ml formulation buffer containing 1 x 10^7 cells with 2 x 10^7 beads attached in a 3 ml syringe for intradermal injections (ID) and intratumoral (IT) injection,
- 3 ml formulation buffer containing 3 x 10^7 cells with 6 x 10^7 beads attached in a 10 ml syringe for intravenous injection (IV) and intratumoral (IT) injection,
- 5 ml of formulation buffer containing  $5 \ge 10^7$  cells attached to  $1 \ge 10^8$  beads in a 10 ml syringe for intravenous infusion (IV).

Note: some cohorts call for a 0.5 ml intradermal dose. For these cohorts, a 1 ml syringe will be provided and the clinic is instructed to administer only 0.5 ml and discard the remaining 0.5 ml.

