### Dosing Schedule A-1: Intradermal and Intravenous Dosing Combined With Cryoablation

The priming step: Subjects will receive an ID injection of AlloStim® (0.5ml) on Days 0, 7, and 14 all in different locations.

The vaccination step: Subjects will receive cryoablation and intratumor (IT) injection of AlloStim® (3 ml) on Day 21.

The activation step: Subjects will receive an IV infusion of AlloStim® (3ml) on Day 28. The booster step: Subjects will receive two (optional) IV booster infusions of AlloStim® (5ml), one on Day 56 and Day 84.

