# Dosing Schedule A-2: Intradermal and Intravenous Dosing With AlloStim® alone

The priming step: Subjects will receive an ID injection of AlloStim® (0.5 ml) on Days 0, 3, 7, 10 and 14.

The vaccination step: Subjects will receive IV AlloStim® (3 ml) on Day 21.

The activation step: Subjects will receive an IV infusion of AlloStim® (3ml) on Day 28.

The booster step: Subjects will receive two IV booster infusions of AlloStim® (3ml), one on Day 49 and another on Day 77.

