#### Title of Study: A Phase I/II study of an experimental therapeutic cancer vaccine created in-situ in subjects with progressive metastatic cancer refractory to standard therapy. ITL-002-CRYO Protocol Number: Study Design: This is a single-arm, open label, single institution Phase I/II study to determine the safety and feasibility of creating an individualized in-situ anti-tumor vaccine. The study protocol has three separate steps: (1) priming step; (2) in-situ vaccination step; and (3) immune stimulation step. Subjects meeting eligibility criteria were primed with at least three and up to nine intradermal AlloStim® injections at a frequency of every 2-8 days at doses between 1 x $10^7$ to 4 x $10^7$ cells. After priming, a selected tumor lesion was cryoablated using a percutaneous, image-guided technique followed by an intratumoral injection of 1-6 x 10^7 AlloStim®. Subjects with palpable tumors also were eligible to receive at least one and up to three alcohol ablation procedures to palpable lesions followed by intratumoral AlloStim®. This was in addition to the cryoablation procedure or in replacement of the cryoablation procedure. At the same time as the intratumoral injections, and/or up to eight days following, the subjects were administered intravenous AlloStim® at doses between 1 x 10^7 to 1 x 10^9 cells. Some subjects with ascites and/or carcinomatosis received intraperitoneal AlloStim® at a dose of 0.5 to 5 x 10^8. Subjects also received intravenous AlloStim® at 1 x 10^7 to 1 x 10^9 cells at the same time or up to 8 days following. Study Purpose: This Phase I/II clinical study was designed to investigate the safety and anti-effect of a personalized anti-tumor vaccine created within the body of subjects with advanced cancers. Study Population: The study population was to consist of up to 50 subjects, 18 years or older, with progressive metastatic cancer refractory to all standard therapy with at least one lesion accessible for percutaneous cryoablation. Study Duration: Total duration of the treatment period for each subject was 90 days. Subjects were evaluated at 30 days after the last AlloStim® treatment for tumor response and again at 60 days and at 90 days. Completed (42 subjects completed the treatment) Study Status:

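### Section 14.4.1 puts 1 × 10⁷ cells in the 0.5 ml intradermal injection, but the supplied syringe holds 1 × 10⁷ cells in 1 ml and half is discarded, so the priming cell dose is two-fold uncertain in both schedules

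*Combined protocol and SAP*

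**What the plan says.** Section 14.4.1 (Intradermal Injection) opens by putting 1 × 10⁷ AlloStim "cells formulated in 0.5ml of 1% human serum albumin in PlasmaLyteA" in each injection, and says that one pre-filled 3 ml syringe is delivered per subject for ID days. Its next paragraph says that for A-1 and A-2, 0.5 ml "will be administered, and the remaining 0.5 ml will be discarded".

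Section 14.1 (Study Drug Formulations) gives the ID dose as 1 × 10⁷ cells with 2 × 10⁷ "beads in 1 ml in a 3 ml syringe". The AlloStim paragraph of the abstract (Section 3) lists the same ID form, and its note on cohorts with a 0.5 ml ID dose says that "a 1 ml syringe will be provided and the clinic is instructed to administer only 0.5 ml and discard the remaining 0.5 ml".

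Section 8 sets priming for A-1 as an ID injection of "0.5ml) on Days 0, 7, and 14 all in different locations" and for A-2 as "0.5 ml) on Days 0, 3, 7, 10 and 14". Both are given as volumes, with no cell count.

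Appendix 3 reports ID doses of 1 × 10⁷ to 4 × 10⁷ cells in the earlier study ITL-002-CRYO.

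**The concern.** The drug's dose is a number of cells, and the volume fixes that number only through the concentration. Section 14.4.1 implies one concentration in its first sentence and Sections 14.1 and 3 state another. This is separate from the A-2 volume conflict (1 ml in the abstract, 0.5 ml in Sections 8 and 14.4.1). It also affects A-1, whose ID volume is 0.5 ml wherever it is given, so settling the A-2 volume would not resolve it.

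Priming is a defined step of both schedules compared in Part 1, and the favored schedule goes on to as many as 25 further subjects in Part 2. Section 14.3 requires the dose to be documented at each use. A site could follow 14.4.1 and record 1 × 10⁷ cells while giving half of a syringe filled to 14.1. The safety and immune results would then be reported against a cell dose that was not the one given. Exposure to the beads, which Section 6.1.1 describes as non-biodegradable, is ambiguous by the same factor. So is the link to earlier experience: one reading sits at the bottom of the ID range in Appendix 3 and the other lies below it.

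**Working it through.** **Inputs**

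- ID syringe as supplied (Sections 3 and 14.1): 1 × 10⁷ cells and 2 × 10⁷ beads in 1 ml.
- ID injection as described in the first sentence of 14.4.1: 1 × 10⁷ cells in 0.5 ml.
- Volume given and volume discarded (14.4.1 and the Section 3 note): 0.5 ml and 0.5 ml, so a 1 ml fill.
- Injections (Section 8): 3 in A-1, 5 in A-2.

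**Formula:** cells delivered = (cells ÷ volume they are formulated in) × volume given.

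**Trying to reproduce the 1 × 10⁷ in 14.4.1 from the supplied syringe:** (1 × 10⁷ ÷ 1 ml) × 0.5 ml = 5 × 10⁶. The stated figure is not reproduced.

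| | Supplied syringe (3, 14.1) | First sentence of 14.4.1 |
|---|---|---|
| Concentration, cells/ml | 1 × 10⁷ | 1 × 10⁷ ÷ 0.5 = 2 × 10⁷ |
| Cells in 0.5 ml | 5 × 10⁶ | 1 × 10⁷ |
| Beads in 0.5 ml (2 per cell) | 1 × 10⁷ | 2 × 10⁷ |
| Cells implied in a 1 ml fill | 1 × 10⁷ | 2 × 10⁷ (not listed) |
| A-1 priming, 3 × 0.5 ml | 1.5 × 10⁷ | 3 × 10⁷ |
| A-2 priming, 5 × 0.5 ml | 2.5 × 10⁷ | 5 × 10⁷ |

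Ratio: (1 × 10⁷) ÷ (5 × 10⁶) = 2.0 in every row.

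**Can any reading reconcile the two?**

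- If 1 × 10⁷ is the content of the whole syringe, the 0.5 ml in the first sentence does not fit, and the discard instruction means half the cells are never given.
- If 1 × 10⁷ is what the subject receives, a 1 ml fill must hold 2 × 10⁷ cells, and no listed form does. The other listed forms are 3 × 10⁷ in 3 ml and 5 × 10⁷ in 5 ml, each 1 × 10⁷ cells/ml.

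**Sensitivity of the totals.** The table uses the Section 8 days and 0.5 ml. Section 14.4.1 lists other ID days: four for A-1 (0, 7, 14, 21) and three for A-2 (0, 7, 14). The abstract gives A-2 1 ml.

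- A-1: from 3 × 5 × 10⁶ = 1.5 × 10⁷ to 4 × 1 × 10⁷ = 4 × 10⁷.
- A-2: from 3 × 5 × 10⁶ = 1.5 × 10⁷ to 5 × 1 × 10⁷ = 5 × 10⁷. The upper end arises either from 0.5 ml at the 14.4.1 concentration or from 1 ml of the supplied syringe. The combination of 1 ml with the unlisted concentration is left out.

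**The case against.** The arithmetic is not contestable, but its weight can be argued.

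- **A lone clause.** Every other stated content, including the intravenous and intratumoral doses in 14.4.2, 14.4.3 and Appendix 1, works out at 1 × 10⁷ cells/ml. Section 14.4.1 also still refers to schedules A-3, A-4 and B to F, which Section 8 does not define, so it carries unrevised text. That is fair as a description of the documents, but it does not settle the dose. The discordant clause stands in the section that instructs the site on giving the injection.
- **Same volume injected.** Within 14.4.1 the site gives 0.5 ml on either reading. This stands: the uncertainty is in cell content and its record.
- **Traceability.** Lot number and dose are recorded under 14.3 and the batch barcode under 14.4.1, so the delivered dose may be recoverable. The CRF, label and batch records are not in the documents, so neither mis-recording nor correct recording can be shown.
- **No analysis by cell dose.** Section 16 summarizes by dosing schedule, and the dose-limiting-toxicity rules count subjects. This also stands: no planned estimate or stopping rule changes. What is affected is the description of the regimen to which the results belong.
- **No excess over earlier exposure.** Neither reading exceeds the earlier ID dose per injection. The gap concerns comparability with that experience more than an unprecedented exposure.

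**Conclusion.** The concern holds. The current text gives two cell contents for the same 0.5 ml ID injection, 5 × 10⁶ and 1 × 10⁷, a factor of exactly 2, and no listed dosage form reconciles them. The conflict applies to A-1 and A-2 alike and lies partly within 14.4.1 itself. The per-injection factor rests only on the 0.5 ml volume that 14.4.1 assigns to both schedules. The two-fold totals also assume the Section 8 days, and the conflicting days and the A-2 volume widen them as shown. The objections limit the consequence to the definition and recording of the regimen; they do not remove the contradiction. Because the cell dose is what was administered and must be documented, it needs correcting. Which figure is right cannot be decided from the documents.

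**What to change.** Reconcile the first two paragraphs of 14.4.1 with each other and with the dosage forms in 14.1 and Section 3. State the ID dose as cells and beads actually administered, beside the concentration, the fill volume and the volume given. Use that same cell figure in Sections 3, 8, 14.1 and 14.4.1, and check that the syringe label and CRF agree. For any subject already dosed, derive the delivered cell dose from the batch record and the recorded volume. The sponsor should confirm the figure from manufacturing records. The ID days in 14.4.1 and the A-2 volume in the abstract should be reconciled with Section 8 in the same amendment, since the cumulative priming dose depends on them.

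The cost is protocol wording and a label and CRF check: no added patients, procedures or assays.
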